10.12 Safety Data

Summaries of safety data will be presented for the SAF analysis set using observed data only, i.e. without imputation. All observed safety data will be listed.

10.12.1 Adverse Events

For this protocol, a reportable AE is any untoward medical occurrence (e.g. sign, symptom, illness, disease or injury) in a patient administered the IP or other protocol-imposed intervention, regardless of attribution. This includes:

- AEs not previously observed in the patient, that emerge during the study.
- Pre-existing medical conditions judged by the Investigator to have worsened in severity or frequency or changed in character during the study.
- Complications that occur as a result of non-drug protocol-imposed interventions.

An adverse drug reaction is any AE for which there is a reasonable possibility that the IP caused the AE. “Reasonable possibility” means there is evidence to suggest a causal relationship between the IP and the AE.

Whenever possible, it is preferable to record a diagnosis as the AE term rather than a series of terms relating to a diagnosis.

All ongoing non-serious AEs, even those which began under SMA-001 study, will be reported from the end of the double-blind study (SMA-001) or from Day 0 for those not randomized to double blind medication in SMA-001 study through the termination visit or at the early termination visit and will be

recorded on the AE page of the eCRF. All ongoing SAEs from SMA-001 study will be reported. The criteria for determining, and the reporting of new SAEs is provided in Study Protocol Section 11.2.

The Investigator should follow all unresolved AEs until the events are resolved or stabilized, the patient is lost to follow-up, or it has been determined that the study treatment or participation is not the cause of the AE. Resolution of AEs (with dates) should be documented on the appropriate CRF page(s) and in the patient's medical record.

The Investigator responsible for the care of the patient or qualified designee will assess AEs for severity, relationship to IP, and seriousness (refer to Protocol Section 11.2 for SAE definition). Severity (as in mild, moderate or severe headache) is not equivalent to seriousness, which is based on patient/event outcome or action criteria usually associated with events that pose a threat to a patient's life or functioning. Seriousness (not severity) serves as a guide for defining regulatory reporting obligations.

The Investigator will determine the severity of each AE using grades defined in [Table 1](#) (the event will be recorded on the source documents and AE CRF). Events that are Grades 4 and 5 are serious events and require completion of both an SAE form and AE CRF.

Table 1 - Categories of Severity for Adverse Events

Severity	Description	
Grade 1	Mild; asymptomatic or mild symptoms; clinical or diagnostic observations only; intervention not indicated.	
Grade 2	Moderate; minimal, local or noninvasive intervention indicated; limiting age-appropriate instrumental ADL*.	
Grade 3	Severe or medically significant but not immediately life-threatening; hospitalization or prolongation of hospitalization indicated; disabling; limiting self-care ADL**.	
Grade 4	Life-threatening consequences; urgent intervention indicated.	Note: Grade 4 and 5 adverse events should always be reported as serious adverse events
Grade 5	Death related to AE.	

Activities of Daily Living (ADL)

* Instrumental ADLs refer to preparing meals, shopping for groceries or clothes, using the telephone, managing money, etc.

** Self-care ADLs refer to bathing, dressing and undressing, feeding self, using the toilet, taking medications, and not bedridden.

A Treatment-Emergent Adverse Event (TEAE) is any AE that emerges after the first dose of study drug for the current Long-Term Study. All AEs will be coded using the Medical Dictionary for Regulatory Activities (MedDRA), Version 23.0. All TEAEs will be summarized. Counts and percentages will be presented for each observed System Organ Class (SOC) and Preferred Term (PT) as defined in MedDRA. A patient having more than one TEAE with the same PT will be counted only once in the incidence calculation for that PT. Similarly, if a patient has more than one TEAE in the same SOC, the patient will be counted only once in the total number of patients with a TEAE for that SOC. Each TEAE will be assessed with respect to severity and relationship to treatment. All AEs will be listed, regardless of whether they were study treatment related.

The relationship of an AE will be recorded using the specified relationship categories described in [Table 2](#).

Table 2 - Description of relationship to adverse events categories

Relationship Category	Description
Not Related	Exposure to the IP has not occurred OR The administration of the IP and the occurrence of the AE are not reasonably related in time OR The AE is considered likely to be related to an etiology other than the use of the IP; that is, there are no facts [evidence] or arguments to suggest a causal relationship to the IP.
Possibly Related	The administration of the IP and the occurrence of the AE are reasonably related in time AND The AE could be explained equally well by factors or causes other than exposure to the IP.
Probably Related	The administration of IP and the occurrence of the AE are reasonably related in time AND The AE is more likely explained by exposure to the IP than by other factors or causes.

The following summary tables will be provided:

1. An overview of TEAEs including the number of TEAEs, related TEAEs, TESAEs, related TESAEs, TEAEs leading to premature discontinuation, TEAEs leading to hospitalization, life-threatening TEAEs, number of patients with at least one TEAE, at least one related TEAE, at least one TESAE, at least one related TESAE, at least one TEAE leading to premature discontinuation, at least one TEAE leading to hospitalization, at least one life-threatening TEAE, and at least one TEAE leading to death
2. Summary of all TEAEs by Primary SOC and PT
3. Summary of all related TEAEs by Primary SOC and PT
4. Summary of all TESAEs by Primary SOC and PT
5. Summary of all related TESAEs by Primary SOC and PT
6. Summary of all TEAEs leading to hospitalization by Primary SOC and PT
7. Summary of all life-threatening TEAEs by Primary SOC and PT
8. Summary of all TEAEs leading to premature discontinuation by Primary SOC and PT
9. Summary of all TEAEs by Primary SOC and PT and maximum severity
10. Summary of all TEAEs by Primary SOC and PT and relationship to treatment.

The following individual data listings will be produced:

1. A listing of all TEAEs
2. A listing of all TESAEs
3. A listing of all IMP related TEAEs
4. A listing of all IMP related TESAEs
5. A listing of all TEAEs leading to hospitalization
6. A listing of all life-threatening TEAEs
7. A listing of TEAEs leading to premature discontinuation
8. A listing of all TEAEs leading to death
9. A listing of all AEs started before the first dose of study drug for the current Long-Term Study

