**CRITERIA FOR EVALUATION:**

**Safety (primary endpoint):**

Safety will be assessed by the incidence of treatment-emergent adverse events (TEAEs), including serious adverse events (SAEs). Vital signs, 12-lead ECGs, clinical laboratory tests, physical examination findings, and concomitant medications will also be evaluated.

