## 10 INVESTIGATIONAL PLAN

### 10.1 Overall Study Design and Plan

This open label outpatient extension study is designed to evaluate the long-term safety, tolerability of amifampridine in patients diagnosed with SMA Type 3. In addition, evaluation of the effects of amifampridine on the QoL will be made. The study will enroll those patients who have completed the SMA-001 study and after all final evaluations for that study have been completed, or those who demonstrated benefit after completing the dose titration period but failed to meet the randomization criteria on Day 0 of SMA-001.

The duration of participation for each patient is expected to be at least 12 months as patients may continue in the study until amifampridine is approved by Regulatory Agencies or the clinical development of amifampridine is terminated for this indication. In addition to amifampridine, patients will continue to receive previous concomitant medications, as needed.

After a new informed consent is signed and inclusion / exclusion criteria for the current protocol are satisfied, eligible patients will be given the optimal dose and dosing schedule that was identified in the Run-in Period from Protocol SMA-001.

The findings from the physical exam (including vital signs, weight); 12-lead ECG; clinical laboratory test results (including pregnancy testing) and any ongoing adverse events will be used as the baseline for the Long-Term safety evaluation.

The efficacy measurement is QoL which will be completed every 3 or 6 months. Safety and tolerability assessments will be made every 3 or 6 months or more frequently at the discretion of the Investigator. The study will continue until amifampridine is approved by Regulatory Agencies or until development of the product for this indication is halted. The Investigator may alter the dose and dosing frequency during the Long-Term Study as well as schedule additional clinic visits for any reason.

Patients will be seen in the clinic at the end of Months 3, 6, 9, 12, 15, 21 and 27 as detailed in the Schedule of Assessments in [Table 1](#) and Section 13. In between the 3-or 6-month visits, patients may also have telephone/video contact with the site, or unscheduled visits, if needed.

Any unused medication must be returned to the clinic at each visit for drug accountability, and an additional supply will be dispensed.

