### 15.3 Primary Endpoint

The primary endpoint of the study is safety and tolerability of amifampridine at Months 3, 6, 9, 12, 15, 21 and 27. For more details see Section [15.5](#) below.

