10.10.2 Duration of Treatment and Compliance

Duration of treatment will be summarized for the SAF analysis set.

The duration of treatment is the (*date of the last study drug dose intake* minus the *date of administration of the first dose of study drug*) +1.

Compliance is 100%*(Number consumed)/(Number prescribed). “Number consumed” is from Study Drug Accountability and “Number prescribed” is number of tablets to have been taken daily duration. Compliance will be summarized for the SAF analysis set.

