No. of TEAEs	n	xx
No. of related TEAEs	n	xx
No. of serious TEAEs	n	xx
No. of serious related TEAEs	n	xx
No. of TEAEs leading to premature discontinuation	n	xx
No. of TEAEs leading to hospitalization	n	xx
No. of life-threatening TEAEs	n	xx
No. of patients with at least one TEAE	n (%)	xx (xx.x%)
No. of patients with at least one related TEAE	n (%)	xx (xx.x%)
No. of patients with at least one TESAE	n (%)	xx (xx.x%)
No. of patients with at least one related TESAE	n (%)	xx (xx.x%)
No. of patients with at least one TEAE leading to premature discontinuation	n (%)	xx (xx.x%)
No. of patients hospitalized due to a TEAE	n (%)	xx (xx.x%)
No. of patients with at least one life-threatening	n (%)	xx (xx.x%)
No. of patients dead	n (%)	xx (xx.x%)

TEAE = any AE started at or after the first dose of study drug for the current Long-Term Study.

TESAE = Treatment Emergent Serious Adverse Events.

Treatment Emergent Adverse Events (TEAE) were defined as "Related" if the relationship to study drug was assessed as "Possible" or "Probable".

Missing relationship category was considered as related to the study drug.

Percentages are calculated relative to the number of patients in SAF population.

N = number of patients, % = percentage of patients.

Source: xxx.sas, Run on ddmmmyyyy

Reference Listings: [16.2.5.1.](#)

Table 14.3.2. Summary of TEAEs by SOC and PT / SAF

	Statistic	Amifampridine (N=XX)
<Primary SOC>		
<PT>	n (%) E	xx (xx.xx%) xx
<PT>	n (%) E	xx (xx.xx%) xx
<PT>	n (%) E	xx (xx.xx%) xx
<Primary SOC>		
<PT>	n (%) E	xx (xx.xx%) xx
<PT>	n (%) E	xx (xx.xx%) xx
<PT>	n (%) E	xx (xx.xx%) xx
<Primary SOC>		
<PT>	n (%) E	xx (xx.xx%) xx
<PT>	n (%) E	xx (xx.xx%) xx
<PT>	n (%) E	xx (xx.xx%) xx
<Primary SOC>		
<PT>	n (%) E	xx (xx.xx%) xx
<PT>	n (%) E	xx (xx.xx%) xx
<PT>	n (%) E	xx (xx.xx%) xx

TEAE = any AE started at or after the first dose of study drug for the current Long-Term Study.

The denominator for the calculation of the percentage is the total number of patients who received the treatment and the numerator is the number of patients who received the treatment with at least one TEAE in the given System Organ Class (SOC)

n = number of patients, % = percentage of patients, E = number of events.

Each patient is counted at most once within each SOC and PT.

Source: xxx.sas, Run on ddmmmyyyy

Reference Listings: [16.2.5.1.](#)

Table 14.3.3. Summary of Related TEAEs by SOC and PT / SAF

	Statistic	Amifampridine (N=XX)
<Primary SOC>		
<PT>	n (%) E	xx (xx.xx%) xx

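### The primary TEAE percentages pool unequal, open-ended follow-up without a rate or an onset period, so they are not a clean estimate of long-term incidence

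*SAP*

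**What the plan says.** **Endpoint.** The protocol synopsis states: "Safety will be assessed by the incidence of treatment-emergent adverse events (TEAEs), including serious adverse events (SAEs". Protocol 15.3 adds: "The primary endpoint of the study is safety and tolerability of amifampridine at Months 3, 6, 9, 12, 15, 21 and 27", and refers to Section 15.5 for the detail.

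**Analysis.** SAP 10.12.1 states: "Counts and percentages will be presented for each observed System Organ Class (SOC) and Preferred Term (PT". The footnotes to the SOC/PT shells (SAP Tables 14.3.2 to 14.3.10) fix the denominator: "The denominator for the calculation of the percentage is the total number of patients who received the treatment". They also define the entries: "n = number of patients, % = percentage of patients, E = number of events". Table 14.3.1 gives event counts and patient counts in the same pooled way. None of the ten tables shows patient-years, a rate or an onset period.

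**Window.** SAP 10.12.1 defines a TEAE as "any AE that emerges after the first dose of study drug for the current Long-Term Study". The definition has a start but no end.

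**Follow-up.** Protocol 10.1 states: "The duration of participation for each patient is expected to be at least 12 months". The synopsis plans about 2 years, the last scheduled visit is Month 27, and the study closes on regulatory approval or when development stops. Protocol 10.2.3 allows withdrawal at any time.

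**Exposure.** SAP 10.10.2 states: "Duration of treatment will be summarized for the SAF analysis set". The result goes to Table 14.2.1 and is not linked to the adverse event tables.

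**The concern.** The primary objective is long-term safety and tolerability. A percentage of all treated patients answers how many had an event while they happened to be observed. Its value depends on the event rate and on how long each patient stayed, and here the second varies between patients and is set partly by an outside event. The same 25% could describe a low rate over two years or a higher one over one year. The pooled tables also do not show whether events arise in the first year or only with prolonged use. Laboratory tests, vital signs, ECG and QoL are all tabulated by visit; TEAEs are not.

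**Working it through.** The documents state no event rate, incidence or dropout figure, so there is no planned number to reproduce. The event rates and the mixed follow-up pattern below are assumptions.

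**Inputs from the documents.** About 12 patients (Protocol synopsis); expected minimum participation 12 months (Protocol 10.1); planned participation about 24 months (synopsis); last scheduled visit Month 27 (Protocol Table 1).

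**Step 1. Spread of follow-up.** The nominal ratio is 24/12 = 2.0 to 27/12 = 2.25. An exit at Month 6 would give 27/6 = 4.5 and an exit at Month 3 would give 27/3 = 9, but nothing in the documents says how many such exits to expect.

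**Step 2. Effect on the crude percentage.** With a constant first-event rate r per patient-year and follow-up of t years, the expected percentage is 100 × (1 − exp(−r·t)).

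| Assumed r | all stop at 12 months (t = 1) | all reach 27 months (t = 2.25) | ratio |
|---|---|---|---|
| 0.10 | 9.5% | 20.1% | 2.1 |
| 0.25 | 22.1% | 43.0% | 1.9 |
| 0.50 | 39.3% | 67.5% | 1.7 |

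For an assumed mix of 6 patients at 27 months, 3 at 12 and 3 at 3, with r = 0.25 (6.1% expected at 3 months), the pooled figure is (6 × 43.0 + 3 × 22.1 + 3 × 6.1)/12 = 28.6%.

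**Step 3. What a rate would add.** Take 3 patients with a first event out of 12. The crude result is 25.0% (exact 95% CI 5.5 to 57.2) whatever the follow-up. The rate is 100 × 3 / patient-years (PY), with exact Poisson limits from chi-square quantiles on 2x and 2x + 2 degrees of freedom, x = 3.

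| Follow-up of the 12 patients | PY | Rate per 100 PY (95% CI) |
|---|---|---|
| all 27 months | 12 × 27/12 = 27.0 | 11.1 (2.3 to 32.5) |
| all 24 months | 12 × 24/12 = 24.0 | 12.5 (2.6 to 36.5) |
| 6 at 27, 3 at 12, 3 at 3 months | (162 + 36 + 9)/12 = 17.25 | 17.4 (3.6 to 50.8) |
| all 12 months | 12 × 12/12 = 12.0 | 25.0 (5.2 to 73.1) |

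These rates count all follow-up as time at risk; a strict first-event rate would stop each patient's clock at the event.

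**Step 4. Is the information lost?** No. Table 14.2.1 gives n and mean treatment days, so total patient-years are n × mean / 365.25. Event counts are in Tables 14.3.1 to 14.3.10. First-dose dates are in Listing 16.2.5.1.1, last-dose dates in Listing 16.2.9 and TEAE onset dates in Listing 16.2.5.1.

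**The case against.** The strongest reply is that nothing is missing except presentation. Event counts, a duration summary, treatment days per patient and dated events are all planned, so with about 12 patients a reader can work out an overall rate and see onset times. There is one arm, no hypothesis and no between-arm comparison to bias. This stands: a reader might infer that the TEAE results will be uninterpretable, and the documents do not support that.

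Other stronger readings also fail:

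- **Several-fold distortion.** This needs many exits near Month 3. No dropout rate is stated, and the nominal spread is 2.0- to 2.25-fold.
- **A month-by-month TEAE analysis was promised and dropped.** Protocol 15.3 defers to 15.5, which asks for summaries by time point for vital signs and laboratory tests but not for adverse events.
- **No comparison with other amifampridine data is possible.** Protocol 8.2 itself reports that experience as crude percentages, for example seizures in 10 of 1,454 (0.69%). The planned percentages are on that scale.
- **The collection period has no end.** Protocol 11.1 collects non-serious events through the termination visit, and 11.2 collects serious events until 4 weeks after the last visit. Only the TEAE definition lacks an end.

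Sampling error also matters. The interval for 3 of 12 (5.5% to 57.2%) is wider than the 22% to 43% shift due to follow-up. That limits precision; it is not a reason to leave the risk period unspecified. It does argue against rates for every preferred term: one event in 24 patient-years gives 4.2 per 100 (95% CI 0.1 to 23.2).

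**Conclusion.** The point holds as a gap in presentation of the primary safety result. The planned percentages mix risk with length of observation and are not a clean estimate of long-term incidence. The effect is about two-fold across the nominal follow-up range: 22% against 43% at 0.25 first events per patient-year. This rests on an assumed constant rate and on the two extremes of all patients stopping at 12 months or all reaching 27; a real mix would fall between them unless many patients leave early. The percentages remain readable next to the counts, durations and listings already planned. This is a cheap improvement, not a flaw that undermines the study.

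**What to change.** 1. Keep all crude percentages.
2. In Table 14.3.1, add total patient-years and events per 100 patient-years with exact Poisson 95% CI for all, related and serious TEAEs. Do not extend this to every preferred term.
3. Add one TEAE overview by onset period, 0-12 and >12 months from the first SMA-002 dose, with the number of patients at risk in each period. A footnote should say that patients had already taken amifampridine for several weeks in SMA-001 (Protocol 8.3), so the first period is not first exposure to the drug.
4. State one end of the TEAE window and use it for both events and patient-time. Treatment duration in SAP 10.10.2 stops at the last dose, while serious events are collected until 4 weeks after the last visit. Events after the last dose should be counted only if patient-time is extended to match.

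**Cost.** A few columns, one small table and one sentence, all from dates already collected. Protocol 15.5 allows additional safety analyses in the SAP, the note in 15.7 lets the SAP prevail without an amendment, and SAP Section 4 foresees revision before the final analyses. The downside is wide intervals with about 12 patients. The Poisson interval also treats events as independent, so it is too narrow if a few patients have many events; a footnote should say so.

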10.12.2 Vital Signs and Body Weight

Analysis will be performed in the SAF analysis set.

Vital signs, including sitting blood pressure (systolic and diastolic; mmHg), sitting heart rate (beats/minute), body temperature (°C), respiration rate (breaths/minute), and weight (kg) will be summarized by time point using descriptive statistics. Changes from baseline will also be summarized by post-dose time point.

Height is recorded at Screening visit only.

BMI will be calculated at Screening visit according to the following formula:

$$BMI (kg/m^2) = ((body\ weight\ (kg))/(height\ (m))^2).$$

Height and BMI will be summarized using descriptive statistics.

10.12.3 12-Lead ECG

Analysis will be performed in the SAF analysis set.

A standard 12-lead ECG will be recorded at Screening, Months 3, 6, 9, 12, 15, 21 and 27 visit.

Each tracing will be classified as “Normal tracing”, “Abnormal tracing (not clinically significant)”, “Abnormal tracing (clinically significant)”, or “Unknown”.

ECG results will be summarized in a shift table with the following shifts presented (baseline versus post dose time point): normal/normal, normal/abnormal NCS, normal/abnormal CS, abnormal NCS/normal, abnormal NCS/abnormal NCS, abnormal NCS/abnormal CS, abnormal CS/normal, abnormal CS/abnormal NCS and abnormal CS/abnormal CS.

Clinically significant changes from baseline will be recorded as AEs.

Abnormalities reported will be coded using MedDRA thesaurus version 23.0, and the terms listed for all enrolled patients.

10.12.4 Physical Examination

Summary analysis will involve the SAF analysis set.

A complete physical examination is to be performed at each clinic visit or, if applicable, at early discontinuation from the study.

These assessments will be summarized by visit using counts and percentages.

All verbatim terms reported in the Physical Examination form will be assigned to a Preferred Term (PT) and will be classified by the primary System Organ Class (SOC) according to the Medical Dictionary for Regulatory Activities (MedDRA) thesaurus, version 23.

A summary table containing the frequency and percentage of patients who exhibited at least one abnormality as well as of the abnormalities reported at each clinic visit by primary SOC and PT will be prepared.

Physical examination abnormalities will be listed for all patients.

10.12.5 Laboratory Tests

For blood chemistry and hematology, descriptive statistics will be presented for the observed value and CFB by time point. In addition, a shift table will be constructed to show the shifts in laboratory results by parameter relative to the normal ranges. The number and percentage of patients with the following shifts will be presented by time point: normal/normal, normal/low, normal/high, low/low, low/normal, low/high, high/low, high/normal, and high/high. The laboratory parameters to be collected are given below in [Table 3](#).

Table 3 - Clinical Laboratory Tests

Blood Chemistry	Hematology	Urine Tests
Albumin	Hemoglobin	Appearance
Alkaline phosphatase	Hematocrit	Color
ALT (SGPT)	WBC count	pH
AST (SGOT)	RBC count	Specific gravity
Direct bilirubin	Platelet count	Ketones
Total bilirubin	Differential cell count	Protein
BUN		Glucose
Calcium		Bilirubin
Chloride		Nitrite
Total cholesterol		Urobilinogen
CO ₂ or bicarbonate		Blood in urine
Creatine phosphokinase		
Creatinine		
Glucose		
GGT		
LDH		
Phosphorus		
Potassium		
Total protein		
Sodium		
Uric acid		

ALT, alanine aminotransferase; AST, aspartate aminotransferase; BUN, blood urea nitrogen; CO₂, carbon dioxide; GGT, gamma-glutamyl transferase; LDH, lactate dehydrogenase; RBC, red blood cell; SGOT, serum glutamic-oxaloacetic transaminase; SGPT, serum glutamic-pyruvic transaminase; WBC, white blood cell.

Urinalysis parameters will not be included in summary tables.

All laboratory parameters will be listed for all patients.

